**9.1.2.11. Subject Global Ratings of Change**

Other Efficacy Statistical Analyses
Endpoint(s)

 
• Subject global rating of change in activity limitation
 
• Subject global rating of change in COPD severity
 

Model Specification

 
• Logistic regression model
 
• Terms in the model:          Dependent : change response (7-point scale)          Categorical : treatment group, smoking status (screening), geographical region
 
• The model will be fit at each visit (Weeks 4, 16, 28, 40 and 52).
 
• Computation of confidence intervals for the odds ratios is based on the individual Wald tests
 

Model Checking & Diagnostics

 
• Refer to Appendix 10: Model Checking and Diagnostics for Statistical Analysis.
 

Model Results Presentation

 
• Number and percentage of subjects reporting each category of change at each visit
 
• Odds ratio, 95% CI and unadjusted p-values for the pairwise treatment comparisons
 

Example SAS Code
<pre>proc logistic data=dsetin;   class trtcd smk region / param=glm;   model changevar = trtcd smk region / l=logit;   [note: both contrast and estimate statements will be used for the pairwise comparisons] run;</pre>

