6.2.10. COPD Assessment Test (CAT)

The CAT will be completed by subjects at screening, randomization, Week 4, Week 28 and Week 52 (or IP Discontinuation Visit).

The COPD Assessment Test (Jones, 2009; Jones, 2012) is a validated, short and simple patient completed questionnaire which has been developed for use in routine clinical practice to measure the health status of patients with COPD. The CAT is an 8-item questionnaire suitable for completion by all patients diagnosed with COPD. When completing the questionnaire, subjects rate their experience on a 6-point scale, ranging from 0 (no impairment) to 5 (maximum impairment) with a scoring range of 0-40. Higher scores indicate greater disease impact.

6.2.11. Subject Global Rating of Activity Limitation and Subject Global Impression of Change in Activity Limitation

Subjects will complete the Global Rating of Activity Limitation at randomisation and all subsequent visits including the final visit (or IP Discontinuation Visit). This single global question will ask subjects to rate their activity limitation on a four-point scale (not limited, slightly limited, limited, very limited).

Subjects will complete a Global Impression of Change in Activity Limitation question at all visits subsequent to randomisation including the final visit (or IP Discontinuation Visit). Response options will be on a 7 point Likert scale ranging from much better to much worse.

(Note: The above assessments are in addition to the subject's daily diary recording of activity level that was affected by their respiratory symptoms.)

6.2.12. Subject Global Rating Severity of COPD and Subject Global Impression of Change in COPD

Subjects will complete the Global rating severity of COPD at randomization. This single global question will ask subjects to rate their severity of COPD on a four point scale (mild, moderate, severe, very severe).

Subjects will complete a Global Rating of Change in COPD (overall disease) question at all visits subsequent to randomisation including the final visit (or IP Discontinuation Visit). Response options will be on a 7 point Likert scale ranging from much better to much worse. Asking at each visit allows for early detection of response as well as continued response.

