**Model Specification**

- Generalized linear mixed model
- Terms in the model:
  - Dependent : response (yes/no)
  - Categorical : treatment group, smoking status (screening), geographical region, visit, subject
  - Continuous : baseline (FEV1, SGRQ total , CAT score or BDI)
  - Interaction : baseline\*visit, treatment group\*visit
- The model will be fit with an unstructured variance-covariance matrix with one single model to include all visits where the assessment in question is scheduled to be performed.
- Computation of confidence intervals for the odds ratios is based on the individual Wald tests.

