**11.4.2. Baseline Definitions & Derivations**

Parameter	Study Assessments Collected Prior to Dosing		Baseline Definition
	Screening	Day 1 Pre-Dose	
Efficacy and Health Outcomes			
Trough FEV1, Trough FVC	X	X	Day 1 pre-dose and pre-bronchodilator nominal time-point
Post-bronchodilator FEV1, Post-bronchodilator FVC	X	X	Day 1 pre-dose and post-bronchodilator nominal time-point
FEV1 reversibility (mL)	X	X	Day 1 FEV1 reversibility (mL)
SGRQ total and domain scores		X	Day 1
CAT score	X	X	Day 1
EQ-5D-5L		X	Day 1
BDI (TDI Baseline)		X	Day 1
Subject global ratings		X	Day 1
Mean number of occasions of rescue use, mean number of nighttime awakenings per night	X	X	Average of measurements from Day -13 to Day 1 inclusive (at least 7 days must be non-missing)
Percentage of rescue-free days, percentage of days symptoms stopped usual activities	X	X	Percentage is calculated as total number of rescue-free days (or total number of days symptoms stopped usual activities) divided by total number of days with non-missing value (from Day -13 to Day 1 inclusive (at least 7 days must be non-missing)) x100
Safety			
Blood pressure	X		Values from most recent assessment prior to first dose of study treatment which records both systolic and diastolic BP (generally Screening but could be a test repeat).
Pulse rate	X		Most recent individual value prior to first dose of study treatment

Parameter	Study Assessments Collected Prior to Dosing		Baseline Definition
	Screening	Day 1 Pre-Dose	
Laboratory tests: Excluding hematology	X		Most recent individual value prior to first dose of study treatment
Laboratory tests: Hematology (including blood eosinophils)	X	X	Most recent individual value prior to first dose of study treatment
ECG endpoints	X		Values from most recent ECG conducted prior to first dose of study treatment

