**11.10.1.7. Logistic Regression**

Endpoint(s)	
 
• Subject global rating of change in activity limitation
 
• Subject global rating of change in COPD severity
 

Analysis	
 
• Logistic regression
 

 
• .
 
• The score test will be used to assess the proportional odds assumption.
 
	

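### The two global-change models leave out the matching baseline ratings; if those ratings predict the response, the odds ratio is pulled towards 1 and some power is lost

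*SAP*

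**What the plan says.** Protocol 6.2.11 pairs a four-point rating of activity limitation with a seven-point impression of change. On the first it says: "Subjects will complete the Global Rating of Activity Limitation at randomisation and all subsequent visits". Protocol 6.2.12 does the same for COPD: "Subjects will complete the Global rating severity of COPD at randomization", again on four points, followed by a seven-point rating of change at every later visit.

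SAP 9.1.2.11 takes "change response (7-point scale" as the dependent variable. Its model terms are "Categorical : treatment group, smoking status (screening), geographical region", and the example code agrees: "model changevar = trtcd smk region / l=logit". A separate model is fitted at each of Weeks 4, 16, 28, 40 and 52. SAP 11.10.1.7 confirms that the model is ordinal: "The score test will be used to assess the proportional odds assumption".

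The baseline table in SAP 11.4.2 has a row for "Subject global ratings" with Day 1 as baseline. SAP Table 5 and the list of displays (Tables 2.098 and 2.100) only summarise the four-point ratings.

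For TDI, SAP 9.1.2.6 uses the trough FEV1 repeated-measures model, which carries a baseline covariate, and SAP 11.4.2 labels the BDI as the TDI baseline. The responder models in SAP 9.1.2.7 name their continuous covariate as "baseline (FEV1, SGRQ total , CAT score or BDI".

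**The concern.** A change rating asks the subject to compare now with then, and where the subject started may well influence the answer. The trial records that starting point for both concepts and gives it a baseline definition, but does not use it in the one analysis where it would serve as a covariate. The SAP's other by-visit models (spirometry, SGRQ, CAT, TDI, diary endpoints, vital signs and QTcF) all adjust for baseline. No reason is given for treating these two endpoints differently.

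At stake is some power for two patient-reported endpoints at five visits. Each is reported with odds ratios, 95% confidence intervals and unadjusted p-values. Protocol 8.3.3.2 allows such results to be declared significant at p<0.05 if both co-primary comparisons succeed.

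**Working it through.** The documents give no sample size, power or effect size for these endpoints, so there is no planned figure to reproduce. The check asks what omitting a four-level baseline rating does to the treatment odds ratio in a cumulative-logit model.

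**Inputs from the documents**
- Arms of 4000, 4000 and 2000 (Protocol 8.2.1).
- Two-sided 0.05, unadjusted (Protocol 8.3.3.2).
- Seven response categories and a four-level baseline rating (Protocol 6.2.11 and 6.2.12).

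**Assumptions, not in the documents**
- Response probabilities of 0.06, 0.16, 0.20, 0.33, 0.13, 0.08 and 0.04 for a comparator subject at the mean baseline rating.
- Baseline rating probabilities of 0.10, 0.30, 0.40 and 0.20.
- Treatment odds ratio, conditional on baseline, of 1.10 (log 0.0953); 1.15 as an alternative.
- Baseline odds ratio per level of exp(0), exp(0.2), exp(0.4), exp(0.7) and exp(1.0), that is 1.00, 1.22, 1.49, 2.01 and 2.72.
- No missing data. Smoking and region are left out of both models, and the rating enters as a linear score.

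**Method.** Expected cell counts were fitted by maximum likelihood with and without the baseline rating, and standard errors were taken from the Fisher information. Then z = log OR / SE, power = Φ(z − 1.96), and relative efficiency = (z unadjusted / z adjusted)².

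**One row in full** (baseline odds ratio 2.01, 4000 vs 4000):
- Unadjusted: z = 0.0887 / 0.0396 = 2.24, power = Φ(0.28) = 61.0%.
- Adjusted: z = 0.0953 / 0.0397 = 2.40, power = Φ(0.44) = 66.9%.
- Relative efficiency: (2.24 / 2.40)² = 0.87.

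**All rows, treatment odds ratio 1.10, 4000 vs 4000**

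| Baseline OR per level | Unadjusted log OR (SE) | Adjusted log OR (SE) | SE ratio, adjusted/unadjusted | Power, unadjusted → adjusted | Relative efficiency |
|---|---|---|---|---|---|
| 1.00 | 0.0953 (0.0398) | 0.0953 (0.0398) | 1.000 | 66.9% → 66.9% | 1.00 |
| 1.22 | 0.0947 (0.0397) | 0.0953 (0.0398) | 1.000 | 66.4% → 66.9% | 0.99 |
| 1.49 | 0.0930 (0.0397) | 0.0953 (0.0398) | 1.001 | 64.9% → 66.9% | 0.95 |
| 2.01 | 0.0887 (0.0396) | 0.0953 (0.0397) | 1.003 | 61.0% → 66.9% | 0.87 |
| 2.72 | 0.0830 (0.0395) | 0.0953 (0.0398) | 1.007 | 55.7% → 66.9% | 0.77 |

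For 4000 vs 2000 the relative efficiencies are the same to two decimals. Adjusted power is 49.9%; unadjusted power is 49.9%, 49.4%, 48.1%, 44.8% and 40.4% down the rows. With a treatment odds ratio of 1.15 and 4000 vs 4000, adjusted power is 94.0% and unadjusted power runs from 94.0% to 86.9%.

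The standard error hardly moves and is, if anything, slightly smaller without the covariate. What moves is the estimate: in the last two rows the odds ratio of 1.10 becomes exp(0.0887) = 1.093 and exp(0.0830) = 1.087.

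**Chance imbalance.** For a baseline category held by half the subjects, the 95% range of the difference between arms is 1.96 × √(0.25/4000 + 0.25/4000) = ±2.2 percentage points, or 1.96 × √(0.25/4000 + 0.25/2000) = ±2.7 points against the smaller arm.

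**The case against.** The strongest case on the other side is that this is a preference and not an error. Randomisation keeps the unadjusted test valid. The SAP sets no rule that every model must adjust for baseline: mortality uses treatment, gender and age (9.1.2.9), and the pneumonia and cardiovascular event models use treatment and region (9.2.13.2). A Day 1 baseline definition does not imply a covariate either, since EQ-5D-5L has one and is only summarised. The change item is a direct rating, not a difference computed from the four-point item, and for COPD the baseline item asks about severity while the change item asks about the disease overall. Adding the rating also changes the quantity estimated, to an odds ratio conditional on baseline. All of this stands as a reason for low priority. It does not amount to a real trade-off, because the model is already conditional on smoking and region and the responder models already adjust for baseline.

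A reader might go further than the documents allow in four ways:
- **That the odds ratios become less precise.** The SE ratios above are 1.000 to 1.007, so adjustment does not narrow the interval on the log-odds scale. The linear-model result that a covariate shrinks the variance does not carry over here.
- **That the loss is certain.** It is zero if the baseline rating does not predict the change response, and the documents do not report that association.
- **That the results are exposed to chance imbalance.** With arms of this size it is limited to about 2 to 3 points, a minor matter.
- **That the SAP contradicts itself.** BDI and TDI form a paired instrument, so the contrast with TDI shows an unexplained difference in practice, not a conflict between sections.

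**Conclusion.** The omission is plain in both text and code, and the SAP does not explain it. Its consequence is conditional: if the baseline rating predicts the change response, the odds ratio is attenuated towards 1 and some power is lost. Under the assumed distributions the relative efficiency of the unadjusted test is 1.00 to 0.77 for baseline odds ratios of 1.0 to 2.7 per level. At a treatment odds ratio of 1.10 and 4000 vs 4000 that is 0 to 11 points of power, and no more than 2 points unless the baseline odds ratio exceeds about 1.5. These figures show a range and do not predict what the trial will find. The attenuation is a move from a conditional to a more marginal odds ratio and does not make the comparison invalid. Both endpoints are other efficacy endpoints outside the hierarchy in SAP 11.9, so this is a low-priority improvement.

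**What to change.** In SAP 9.1.2.11, pre-specify the Day 1 Subject Global Rating of Activity Limitation as a categorical covariate in the activity-change model, and the Day 1 Subject Global Rating of Severity of COPD in the COPD-change model. Add each to the listed model terms and to the CLASS and MODEL statements of the example code, with a reference to the baseline definition in SAP 11.4.2. If the sponsor prefers the unadjusted model, one sentence giving the reason would do.

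The data are already collected. Three small costs should be acknowledged:
- Subjects with a missing baseline rating drop out of the model.
- The odds ratio becomes conditional on the baseline rating, so the term should be fixed before unblinding.
- The proportional-odds check in SAP 11.10.1.7 then covers the added term as well, and that section names no fallback if the check fails.

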## 9.2. Safety Analyses

### 9.2.1. Overview of Planned Analyses

The safety analyses will be based on the ITT population unless stated otherwise.

Section 9.2.2 to Section 9.2.12 provide the overviews of the planned safety analyses, with the detailed list of data displays being presented in Section 11.12.

### 9.2.2. Overview of Planned Exposure Analyses

**Table 6 Overview of Planned Exposure Analyses**

	Data Displays Generated		
	Table	Figure	Listing
Exposure			
Exposure Data	Y 	Y	Y
Post-treatment Duration on Study	Y 		Y
On and Post-treatment Duration on Study	Y 		Y

**NOTES :**

- T = Table, F = Figure, L = Listing, Y = Yes display generated.
  - Stats Analysis = Represents TFL related to any formal statistical analyses (i.e. modeling) conducted.
  - Summary = Represents TFL related to any summaries (i.e. descriptive statistics) of the observed raw data.
  - Individual = Represents FL related to any displays of individual subject observed raw data.
1. Repeat by eosinophil subgroup

### 9.2.3. Overview of Planned Adverse Event Analyses

**Table 7 Overview of Planned Adverse Event Analyses**

	Data Displays Generated		
	Table	Figure	Listing
Adverse Events (AEs)			
Overview of On-treatment AEs	Y		
All AEs (ASE)			Y
On-treatment AEs	Y 		
On-treatment Drug-Related AEs	Y		
On-treatment AEs Leading to Permanent Discontinuation of Study Treatment or Withdrawal from the Study	Y		Y 
Ten Most Frequent On-treatment AEs in Each Treatment Group	Y		
On-treatment Common Non-Serious AEs (3% or More of Subjects in Any Treatment Group)	Y		
On-treatment AE Categories of Interest in the Elderly by Age	Y		
Relationship of AE System Organ Class, Preferred Term and Verbatim Text (ASE)	Y		
Subject Numbers for Individual AEs (ASE)			Y
Serious Adverse Events (SAEs)			
Pre-treatment SAEs	Y 		Y 
Pre-treatment Fatal SAEs (ASE)	Y		
Pre-treatment SAEs Leading to Withdrawal from Study (ASE)	Y		

	Data Displays Generated		
	Table	Figure	Listing
Subjects and Number of Occurrences of on-treatment serious, drug-related serious, fatal and drug-related SAEs	Y		
On-treatment SAE	Y 		Y 
On-treatment Drug-Related SAEs	Y		
On-treatment Drug-Related Fatal SAEs	Y		
Post-treatment SAEs	Y		Y 
Post-treatment Fatal SAEs	Y		
Reasons for Considering as a Serious AE			Y
Adjudicated Serious Adverse Reports			
Adjudicated On-treatment Serious Adverse Reports	Y 		
Adjudicated Post-treatment Serious Adverse Reports	Y 		
AEs of Special Interest (AESI)			
On-treatment AESI	Y 		
Analysis of Time to First On-treatment Event in the Pneumonia AESI Group	Y 	Y 	
Pneumonia Risk Factors at Screening for those Subjects with an on-treatment event in the pneumonia AESI group	Y 		
Analysis of Time to First On-treatment Event in the CV AESI Group	Y 	Y 	
Summary of Incidence of On-treatment Pneumonia AESI and Adjudicated Pneumonia	Y		
SAEs of Special Interest (SAESI)			
On-treatment Serious AESI	Y 		
Analysis of Time to First On-treatment event in the Pneumonia AESI group resulting in hospitalization, prolonged hospitalization or death	Y 	Y 	
Analysis of Time to First On-treatment event in the CV AESI group resulting in hospitalization, prolonged hospitalization or death	Y 	Y 	

**NOTES :**

- T = Table, F = Figure, L = Listing, Y = Yes display generated.
  - Stats Analysis = Represents TFL related to any formal statistical analyses (i.e. modeling) conducted.
  - Summary = Represents TFL related to any summaries (i.e. descriptive statistics) of the observed raw data.
  - Individual = Represents FL related to any displays of individual subject observed raw data.
1. Repeat by country
  2. Repeat for ASE population
  3. Repeat for fatal and non-fatal separately
  4. Cox proportional hazards analysis and Kaplan-Meier plot for time to first event
  5. Combined listing for all reported AEs (any treatment phase). SAE listing will be split by fatal and non-fatal SAEs and based on the ASE population
  6. Repeat by eosinophil subgroup
  7. Additional Kaplan-Meier plot for UMEC/VI and FF/VI treatment groups only

**9.2.3.1. Adverse Events of Special Interest**

Adverse events of special interest (AESI) have been defined as AEs which have specified areas of interest for FF, VI, or UMEC or for the COPD population. A list of Standardized Medical Dictionary for Regulatory Activities (MedDRA) Queries (SMQs) and other groupings for AESI is provided in Section [11.5.4.2](#).

A summary of AE categories of interest in the elderly by age and overall for each treatment group will be provided for AESI. The list of AE categories of interest in the elderly is provided in Section 11.5.4.2.

A summary of the number of events in the pneumonia AESI group and the number of these that had investigator-reported pneumonia (on the pneumonia eCRF form, and split by those supported/not supported by x-ray/CT scan) and/or that had an associated adjudicated report of pneumonia will be provided. This will be repeated for serious events in the pneumonia AESI group within the same table. The number of investigator-reported pneumonia events not reported as pneumonia AESI will also be provided and the number of adjudicated serious adverse reports of pneumonia not associated with a pneumonia AESI. Association between events in the pneumonia AESI group and adjudicated reports of pneumonia is defined in Section 11.5.4.2.

**9.2.3.2. Pneumonia Risk Factors**

Baseline characteristics to identify potential pneumonia risk factors at screening, as defined in Section 11.5.2.5, will be summarised for those subjects who have an on-treatment event in the pneumonia AESI group.

